## 5. Investigation Plan

### 5.1. Study Design

The REVAMP Clinical Study will be a multi-center, prospective, randomized, single-blinded, clinical feasibility study. Subjects will be randomized in a 2:1 ratio to elevated night pacing ON or elevated night pacing OFF.

It is expected that up to 50 subjects may be enrolled to ensure 30 subjects undergo elevated night pacing at approximately 10 sites in the United States to ensure enrollment completion within the pre-specified timeframe.

[figure not shown]
The REVAMP study will be conducted as a Non-Significant Risk (NSR) IDE study. The REVAMP Research System does not include an investigational device; the ability to program a lower rate of 100 bpm is available in market-released pacemakers, and the Sleep function (which allows a different rate to be programmed for part of a 24-hour clock) is an approved feature in market-released pacemakers that will be used in the clinical study. The study will be conducted in compliance with 21 CFR Parts 11, 50, 56, 812.2(b)(1). This study does not require an IDE submission to FDA.

The Sleep Function will be programmed so that the pacemaker can deliver an elevated pacing rate of 100 bpm during the night for 5 hours and lower the rate during the daytime hours. This is within the FDA-approved programmable parameters of the Sleep Function feature.

The study will collect the following information: demographics, medical history, medications, standard physical, NYHA class, blood samples to measure NT-proBNP, Troponin and other biomarkers, echo

measurements, MN Living with Heart Failure Questionnaire, EQ-5D-5L Questionnaire, 6 Minute Walk Test, implanted device information, device interrogations, save-to-media, adverse events (including death), system modifications, and exit information. The MN Living with Heart Failure Questionnaire was chosen to measure the quality of life for subjects with heart failure, which includes a question on how well the subject is sleeping at night.

**Figure 1: In Office Study Visits**

## 5.2. Study Population

This study will enroll patients who have a Medtronic dual chamber pacemaker system with the Sleep function per local guidelines and who meet all of the specific study inclusion criteria and none of the exclusion criteria.

All subjects in this investigation have received a Medtronic dual chamber pacemaker for approved indications. HFpEF subjects who have a small to normal LV volume and evidence of LV hypertrophy and/or increased LV wall thickness will be selected for this study.

## 5.3. Study Procedures

Clinical data is collected at designated time points throughout the study as indicated in Table 1 below. Data will be collected using eCRFs, an electronic data management system for clinical studies. At the baseline, 4 week, 8 week, and 12 week visits subjects are to fill out the MN Living with Heart Failure Questionnaire and perform a 6 Minute Walk Test. At the same visits, an echocardiogram must be done, for which instructions are provided in an Echocardiography Handbook (provided under separate cover). A blood draw must also be done, (instructions are provided under separate cover.) The device programming should occur after all other study procedures are complete, except for the final device interrogation and save-to-media. The EQ-5D-5L Questionnaire will only be collected at the Baseline and 8 week visits.

In addition to eCRF data, non-eCRF data will be collected to include device interrogation files/save-to-media and digital echo data.

**Table 1: Study Procedures**

Study Procedure	Enrollment	Baseline	Telephone Call Follow Up Visits (24 Hour, 5 days, 2 weeks, 6 weeks, 10 weeks)	4 week visit	8 week visit	12 week visit (Study Exit)	Early Study Exit	Unscheduled Visit
Informed consent	x							
Inclusion/exclusion	x	x						
Demographics		x						
Medical History		x						
Medications		x	x	x	x	x	x	x**

# REVAMP Statistical Analysis Plan

Revision 2

Page 13 of 41

Medtronic

Study Procedure	Enroll- ment	Baseline	Telephone Call Follow Up Visits (24 Hour, 5 days, 2 weeks, 6 weeks, 10 weeks)	4 week visit	8 week visit	12 week visit (Study Exit)	Early Study Exit	Unscheduled Visit
Physical Assessment		x		x	x	x		x**
NYHA class		x		x	x	x		
MN Living with Heart Failure Questionnaire		x		x	x	x		
EQ-5D-5L Questionnaire		x			x			
6 Minute Walk Test		x		x	x	x		
Echo		x		x	x	x		x**
Blood Draw		x		x	x	x		x**
Initial Device Interrogation/Save- to-media		x		x	x	x	x	x**
Device Programming		x		x*	x*		x**	x**
Final Device Interrogation/ Save-to-Media		x		x	x	x	x	x**
At least 30 minute observation period post device programming		x						
Symptom Assessment			x	x	x	x		x**
Heart Rate (using finger oximeter)			x					
Crossover				As they occur				
System modifications				As they occur				

Study Procedure	Enroll- ment	Baseline	Telephone Call Follow Up Visits (24 Hour, 5 days, 2 weeks, 6 weeks, 10 weeks)	4 week visit	8 week visit	12 week visit (Study Exit)	Early Study Exit	Unscheduled Visit
Adverse events (AEs)/Death								As they occur
Device Deficiencies								As they occur
Study deviations								As they occur
Study Exits								As they occur

[figure not shown]
\* See programming recommendations for the follow up visit

\*\* If deemed necessary by the investigator

[figure not shown]
## 6. Determination of Sample Size

[figure not shown]
As a feasibility study, this study is not powered to meet any specific endpoints. While this feasibility study is not powered to formally test a hypothesis, it is expected that a sample of up to 30 subjects will be sufficient to determine whether this approach warrants further study. The 4 week safety and tolerability objective described in Section 7.9.1 will help determine whether to move forward with this therapy. Figure 2 indicates that improvements in the confidence interval width at various proportions of subjects meeting the 4 week safety and tolerability endpoint beyond 30 subjects are relatively small.

**Figure 2: 95% Confidence Interval Widths for Various Proportions of 4 Week Safety and Tolerability Endpoint**

## C.I. Width vs N with C.L.=0.95 P=0.700 C.I. One Proportion

## 7. Statistical Methods

### 7.1. Study Subjects

#### 7.1.1. Disposition of Subjects

Subject disposition will be summarized by a CONSORT flow diagram, based on the subject flow diagram shown in Figure 1, but providing additional details on subject attrition.

#### 7.1.2. Clinical Investigation Plan (CIP) Deviations

A study deviation is defined as an event within a study that did not occur according to the Clinical Investigation Plan or the Clinical Trial Agreement.

Prior approval by Medtronic is expected in situations where the investigator anticipates, contemplates, or makes a conscious decision to deviate. Prior approval is not required when a deviation is necessary to protect the safety, rights or well-being of a subject in an emergency or in unforeseen situations beyond the investigator's control (e.g. subject failure to attend scheduled follow-up visits, inadvertent loss of data due to computer malfunction, inability to perform required procedures due to subject illness, blood sample or echo lost at Core Lab).

For medically justifiable conditions which preempt a subject's ability to complete a study-required procedure, it may be permitted to report only one deviation which will apply to all visits going forward. This may also apply for other unforeseen situations (e.g. the subject permanently refuses to complete a study required procedure and the data will not contribute to the primary endpoint analysis). However, prior approval from Medtronic is required for such situations.

All study deviations must be reported to Medtronic regardless of whether they are medically justifiable, pre-approved by Medtronic, an inadvertent occurrence, or taken to protect the subject in an emergency. The deviation must be recorded in Oracle Clinical. Refer to the CIP for an explanation for the deviations.

In the event the deviation involves a failure to obtain a subject's informed consent, or is made to protect the life or physical well-being of a subject in an emergency, the deviation must be reported to the IRB as well as Medtronic as soon as possible but no later than five (5) working days, or according to local requirements. Reporting of all other study deviations should comply with the IRB policies and/or local laws and deviations must be reported to Medtronic as soon as possible upon the site becoming aware of the deviation.

Medtronic is responsible for analyzing deviations, assessing their significance, and identifying any additional corrective and/or preventive actions (e.g. amend the Clinical Investigation Plan, conduct additional training, terminate the study). Repetitive or serious investigator compliance issues may result in initiation of a corrective action plan with the investigator and site, and in some cases, necessitate suspending enrollment until the problem is resolved or ultimately terminating the investigator's participation in the study. Medtronic may provide site-specific reports to investigators summarizing information on deviations that occurred at the investigational site on a periodic basis.

### **7.1.3. Analysis Sets**

A set of analysis datasets will be created based on case report forms (enrollment, baseline, randomization). Flagging variables will indicate whether a subject passed various study milestones, such as whether the subject could tolerate the study therapy at baseline visit testing and initiated the study therapy.

## **7.2. General Methodology**

Medtronic employees or designees will perform all statistical analyses. Additional exploratory analyses of the data may be conducted as deemed appropriate. Data analysis may be carried out throughout the study without having all enrolled subjects completing study required follow-ups.

### **7.3. Center Pooling**

Centers/investigators will be pooled for analysis of study objectives.

### **7.4. Handling of Missing, Unused, and Spurious Data and Dropouts**

Missing data imputation methods will not be used for the study objectives unless specified otherwise within the analysis methods.

## 7.5. Adjustments for Multiple Comparisons

No adjustments are planned for multiple comparisons.

## 7.6. Demographic and Other Baseline Characteristics

Baseline characteristics and relevant medical history will be collected on eCRFs for all enrolled subjects. Baseline characteristics will be summarized for all enrolled subjects. Baseline variables to be summarized may include, but are not limited to: age, sex, race, height, weight, NYHA, medical history (symptoms) and general cardiovascular history. Baseline blood and echo measurements will be summarized from data sets prepared by the blood and echo core labs, respectively.

For continuous variables, mean, standard deviation, median, and range will be reported. For categorical variables, frequency and percentage will be reported.

## 7.7. Treatment Characteristics

After enrollment in the REVAMP clinical study, at each protocol required follow-up, the investigator must evaluate the subject's health, assess for any adverse events or medication changes, and interrogate the study device to verify appropriate study device function.

## 7.8. Interim Analyses

Abstracts, posters and presentations could be generated on this dataset throughout the study. No type I error correction or alpha spending will be performed for analyses conducted in support of deliverables occurring while the study is ongoing.

## 7.9. Evaluation of Objectives

### 7.9.1. Ancillary Safety and Tolerability Endpoint

#### **Safety and Tolerability – 4 weeks**

##### Hypothesis

A 4 week period of elevated night pacing is safe and tolerable.

##### Analysis Methods

The proportion of subjects who remain in the study up until the 4 week visit without exiting due to intolerable symptoms, increase in NT-proBNP levels, decrease in LVEF or increase in troponin will be calculated along with the lower bound of the one-sided 95% confidence interval.

As the REVAMP study was designed to explore the feasibility of the study therapy, there was no pre-specified threshold for overall safety and tolerability. In order to provide the most conservative estimate of the safety and tolerability, any study exit prior to the 4 week visit will be assumed to be related to intolerable symptoms or safety issue. Also, study

deaths attributed by the investigative site as related or unknown relative to the study therapy prior to the 4 week visit will be counted against the proportion of subjects remaining in the study. A variable active4wk will be set to equal 1 for subjects who remain in the study up until the 4 week visit and will be set to equal 0 otherwise. The proportion of subjects remaining in the study, along with the lower bound of the one-sided 95% confidence interval can be found using code similar to:

```
PROC FREQ DATA=Revamp_Test;
  TABLE active4wk / BINOMIAL(EXACT LEVEL='1') ALPHA=0.1;
RUN;
```

As this study is exploring the feasibility of the study therapy, sensitivity analysis may be performed, exploring various assumptions regarding ambiguous study exits.

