### 10.11. Randomization (4 Week Follow-Up)

Subjects will be assigned to a group at random during the randomization visit. Randomization will occur at 4 weeks.

Subjects will be randomized in a 2:1 ratio to the Elevated Night Pacing ON or to the Elevated Night Pacing OFF group.

Sites will receive this randomization assignment from the randomization schedule, which is automatically populated on the eCRF.

Procedures to be performed and data to be collected at Randomization include:

- Physical Assessment (including weight, heart rate, symptoms, and blood pressure)
- Medications
- NYHA Class
- MN Living with Heart Failure Questionnaire
- 6 Minute Walk Test
- Echo\*
- Blood Draw\*\*
- Randomization assignment
- Device Interrogation/ (initial)
- Save-to-Media (initial)
- Device Programming, see Table 7: Programming Recommendations at 4 Week Follow-Up
- Device Interrogation (final) - this needs to be completed at the end of the visit after programming has been completed
- Save-to-Media (final)
- Adverse Events (report new/assess ongoing AEs), Study Deviations, System Modifications, Device Deficiencies, Crossovers (as they occur)

\*The echo must be sent to the Echo Core Laboratory for analysis, with a copy of the echo remaining at the site. Details of the Echo Core Laboratory, type of echo to be performed, and the review process will be provided in an Echocardiography Handbook (provided under separate cover).

\*\* The blood sample must be sent to the Blood Core Laboratory for analysis. Details of the blood core lab and the blood draw process will be provided under separate cover.

For any subject who has an abnormal NT-proBNP, troponin or LVEF measurement as defined in the Safety Assessment (Section 10.19. Assessment of Safety) and the investigator elects to discontinue elevated night pacing, a subsequent visit will be necessary for the elevated night pacing to be programmed OFF if the subject was randomized to the elevated pacing ON arm. The subject should continue to be followed through the 12 week visit.

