### **10.19. Assessment of Safety**

As a feasibility study, the primary objective is to assess the feasibility of using elevated night pacing as a therapy for heart failure with preserved ejection fraction. This includes assessing the safety and tolerability of elevated night pacing, as described in Section 5.1. Background. Subjects who experience intolerable symptoms from the elevated pacing therapy and whose symptoms cannot be reconciled by reprogramming may have the elevated night pacing programmed OFF. NT-proBNP, troponin, assessed from peripheral blood samples and LVEF, as assessed by the echo, will be collected at Baseline and at the 4 week visit. Subjects with increases in NT-proBNP and troponin from Baseline to the 4 week visit should be monitored by the investigator for accompanying symptoms, including worsening heart failure and cardiac ischemia. Symptoms should be reported as adverse events and subjects will be considered for withdrawal from the study, at the discretion of the investigator. Subjects with 4 week LVEF < 45% whose baseline LVEF was at least 55% may also be considered for withdrawal from the study at the discretion of the investigator. NT-proBNP, troponin and LVEF will be further assessed as discussed in Section 10.11. Randomization (4 Week Follow-Up) and Section 14.1.2. Ancillary Safety Endpoint – NT-proBNP, troponin, LVEF. Further information on the collection of Adverse Events is discussed in Section 12.5. Reporting of Adverse Events.

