##### Analysis Methods

The proportion of subjects who remain in the study up until the 4 week visit without exiting due to intolerable symptoms, increase in NT-proBNP levels, decrease in LVEF or increase in troponin will be calculated along with the lower bound of the one-sided 95% confidence interval

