##### Analysis Methods

The proportion of subjects who remain in the study from the 4 week visit to the 8 week visit without exiting due to intolerable symptoms, increase in NT-proBNP levels, decrease in LVEF or increase in troponin will be calculated along with the lower bound of the one-sided 95% confidence interval for both arms (elevated night pacing left ON versus elevated night pacing programmed OFF).

This analysis will be similar to the 4 week safety and tolerability endpoint, using a variable active8wk to indicate whether a subject remains in the study up until the 8 week visit. The same conservative approach to study exits and death used for the 4 week time point will be implemented for the 8 week time point. The proportion of subjects remaining in the study,

along with the lower bound of the one-sided 95% confidence interval can be found using code similar to:

```
PROC FREQ;
  TABLE active8wk / BINOMIAL(EXACT LEVEL='1') ALPHA=0.1;
RUN;
```

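### The 4-week safety and tolerability proportion closes at the visit where NT-proBNP, troponin and LVEF are first re-measured, so three of its four named failure reasons cannot normally register

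*SAP*

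**What the plan says.** **Endpoint.** Under protocol 14.1.1, success means that a subject must "remain in the study up until the 4 week visit without exiting due to intolerable symptoms, increase in NT-proBNP levels, decrease in LVEF". A troponin rise is the fourth named reason. SAP 7.9.1 repeats this. The set is every enrolled subject programmed with elevated night pacing.

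**Coding.** "A variable active4wk will be set to equal 1 for subjects who remain in the study up until the 4 week visit", and 0 otherwise. To be conservative, "any study exit prior to the 4 week visit will be assumed to be related to intolerable symptoms or safety issue". Deaths before that visit that the site judges related to the therapy, or of unknown relation, also count against the proportion.

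**Measurement.** Protocol 10.19 says that NT-proBNP, troponin and LVEF "will be collected at Baseline and at the 4 week visit". Protocol Table 4 and SAP Table 1 agree.

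**Action.** Under protocol 10.11, if the investigator elects to stop pacing on an abnormal week-4 result, "a subsequent visit will be necessary for the elevated night pacing to be programmed OFF" for a subject randomised ON, and follow-up continues to week 12. Protocol 10.19 allows withdrawal to be considered on the same week-4 values.

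**Next period.** The 8-week proportion runs from the 4 week visit to the 8 week visit, by arm. "The same conservative approach to study exits and death used for the 4 week time point will be implemented for the 8 week time point".

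**Use.** SAP 6: "The 4 week safety and tolerability objective described in Section 7.9.1 will help determine whether to move forward with this therapy".

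**The concern.** The endpoint names four reasons for failure, but its clock stops at the visit where three of them are next measured. A subject whose week-4 troponin leads the investigator to stop therapy has already scored active4wk = 1.

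This does not fit the plan's own intent. Protocol 7.2 describes a safety assessment at the 4 week visit, with NT-proBNP as the signal for worsening heart failure and troponin for ischemia. Protocol 14 presents the 8-week comparison as one among subjects in whom the first four weeks proved safe and tolerable. Yet a subject whose week-4 results later prompt stopping enters that comparison as having finished the first period.

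At stake is a proportion that informs the decision to continue with the therapy and supplies the precision argument for 30 subjects. As built, it reflects early retention and symptom tolerance. The week-4 safety results cannot lower it.

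**Working it through.** **1. Timing, from the documents.**

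- Baseline: blood draw and echo (protocol Table 4).
- Between Baseline and week 4: phone calls at 24 hours, 5 days and 2 weeks, covering symptoms, medications and heart rate (protocol 10.10). No blood draw or echo is scheduled. Either may be done at an unscheduled visit at the investigator's discretion (protocol 10.13).
- 4 week visit: blood draw and echo, sent to core laboratories; randomisation and programming take place at the same visit (protocol 10.11).
- Endpoint window: exits before the 4 week visit (SAP 7.9.1).

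The number of scheduled post-baseline NT-proBNP, troponin or LVEF values inside the window is therefore zero. Even a same-day reading would not cause an exit before the visit.

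**2. Where a week-4-triggered case goes.**

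| What happens after the week-4 result | 4-week proportion | 8-week proportion |
|---|---|---|
| Subject withdrawn before week 8 | success | failure in the arm drawn, ON or OFF |
| ON subject: pacing stopped, follow-up continues | success | success |
| OFF subject: pacing already off, stays in follow-up | success | success |

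**3. The plan's own figures.** The sample of up to 30 is supported only by interval width, with no target width stated, so it cannot be derived. Two-sided 95% exact widths at a proportion of 0.70 are 0.424 (n = 20), 0.347 (30), 0.300 (40) and 0.267 (50), which fits the statement that gains beyond 30 are relatively small. ALPHA=0.1 in the SAS code gives 0.1/2 = 0.05 per side, which matches the stated one-sided 95% bound.

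**4. Size.** The exact lower bound L for x successes in n solves P(X ≥ x | n, L) = 0.05. When x = n this is L = 0.05^(1/n), so 30/30 gives 0.05^(1/30) = 0.905.

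Let k be the number of subjects withdrawn, or taken off pacing, because of a week-4 result. The documents give no value for k, so it is an assumption shown as a range. With n = 30 and no earlier exits, the plan reports 30/30 and 90.5% for every k. Counting the k subjects:

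| k | Proportion | Lower bound | Fall from 90.5% |
|---|---|---|---|
| 1 | 29/30 = 96.7% | 85.1% | 5.4 points |
| 3 | 27/30 = 90.0% | 76.1% | 14.4 points |
| 6 | 24/30 = 80.0% | 64.3% | 26.2 points |

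With 2 symptom exits before week 4, the plan reports 28/30 (80.5%). Counting k = 2 gives 26/30 (72.0%), and k = 4 gives 24/30 (64.3%).

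**5. Effect on weeks 4 to 8.** Allocating 30 subjects 2:1 gives 20 ON and 10 OFF, assuming no earlier loss. One displaced withdrawal moves ON from 20/20 (bound 86.1%) to 19/20 (78.4%), or OFF from 10/10 (74.1%) to 9/10 (60.6%). If withdrawal does not depend on arm, one third of such cases are expected in OFF.

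**The case against.** Several points on the other side stand and limit the claim.

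- **The exit rule is broad.** A reader might infer that only exits for the four named reasons count. The SAP counts any exit before the 4 week visit. That is conservative for early exits, but neither it nor the optional sensitivity analysis of ambiguous exits reaches a decision made after the visit.
- **The data are not lost.** A reader might infer that week-4 abnormalities vanish from the analysis. They are missing only from the two retention proportions. SAP 7.9.2 tests mean change from baseline to week 4 in all three measures, and protocol 10.19 has accompanying symptoms reported as adverse events. A mean change does not, however, show how many subjects had to stop.
- **It is not impossible in every case.** A discretionary unscheduled blood draw or echo could prompt an earlier exit.
- **The 8-week comparison is not shown to be biased.** Randomisation precedes action on the results, so harm from the shared first period is balanced across arms in expectation. It dilutes the contrast. The plan gives only a bound per arm for these proportions, with no formal test.
- **The illustration covers two things.** If all k subjects are exits, the fall is purely one of timing. A subject taken off pacing but kept in follow-up would be missed by an exit-based endpoint even with perfect timing.
- **The endpoint is ancillary.** It has no threshold, and SAP 6 says only that it will help in the decision, not that it settles it.

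**Conclusion.** The point holds in this form: the 4-week proportion names three failure reasons that its window normally excludes. Withdrawals prompted by week-4 results move to the 8-week proportion of either arm, and subjects who remain in follow-up, ON or OFF, register in neither.

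With 30 subjects and no earlier exits, the reported lower bound is higher by 5.4 points for one such subject and by 14.4 points for three. These sizes depend on the assumed number of cases; the timing fault does not.

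This should be fixed, but it does not invalidate the study. The endpoint is ancillary and unpowered, and the underlying values are analysed elsewhere.

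**What to change.** In SAP 7.9.1 and protocol 14.1.1:

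1. Set active4wk = 0 also for any subject whose week-4 NT-proBNP, troponin or LVEF result led to withdrawal or to a decision to discontinue elevated night pacing, whenever acted on up to a stated cut-off (for example the 8 week visit). Report week-4-triggered exits and therapy stops separately, so that timing and the choice of event can be told apart.
2. Record the investigator's assessment of the week-4 results by the same question for every subject, preferably without reference to the assignment. Only subjects are blinded (protocol 10.11.1), and for an OFF subject the answer is hypothetical. Show the 4-week result with and without OFF subjects counted on that assessment alone.
3. Keep all randomised subjects in the 8-week proportions by arm and flag the week-4-triggered cases there. Exclude them only in a sensitivity analysis. The existing 8-week exclusion concerns failures during the first four weeks; removing subjects on decisions made after randomisation could bias the ON-versus-OFF comparison.

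Separately, protocol 10.11 (pacing off if the investigator so elects, with follow-up to week 12), 10.19 (withdrawal considered at the investigator's discretion) and Table 9 (pacing programmed off if levels worsen) describe different handling of an abnormal result and must be reconciled. This review takes no position on which is right.

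Cost: wording in both documents and one eCRF field, with no new tests. The 4-week proportion may look less favourable and becomes final later.

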## **10.15. Study Exit**

Subjects will be exited from the study for any of the following situations:

- Study completed
- Subject death
- Subject lost to follow-up
- Subject chooses to exit (i.e. revokes informed consent)
- Investigator withdraws subject
- Subject has intolerable symptoms that cannot be alleviated by reprogramming

A Study Exit eCRF needs to be completed for all subjects with the date and reason for the exit. The following should also be collected if applicable:

- Scheduled/Unscheduled Follow Up eCRF, if applicable
- Adverse Events, Study Deviations, System Modifications, Device Deficiencies

The finger pulse oximeter should be returned to the site at the study exit visit. After all study tests and procedures have been completed and just prior to subject exit from the study, the subject may be informed (verbally or in written form) of the subject's randomization assignment.

Following exit, subjects will continue to receive standard medical care and should be managed and followed per physician discretion. There will be no further required study-related follow-up visits for these subjects.

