### **12.1. Adverse Events**

Adverse Event definitions are provided in Table 10. To ensure that all AEs that are potentially relevant are collected, the following will be collected throughout the study duration, starting at the time of signing the Informed Consent Form:

- All system related AEs
- All programming related AEs
- All cardiovascular related AEs
- All Serious Adverse Events (SAEs), regardless of relatedness

In order to fully understand intolerable symptoms and mitigate any safety concerns about elevated night pacing, for any subject that exits the study because of intolerable symptoms, the enrolling site should report any associated programming related AEs. Reporting of these events to Medtronic will occur on an Adverse Event (AE) eCRF. Documented pre-existing conditions are not considered AEs unless the nature or severity of the condition has worsened.

For AEs that require immediate reporting (see Table 12), initial reporting may be done by phone, fax, or on the eCRF completing as much information as possible. The original completed AE eCRF must be submitted to Medtronic as soon as possible.

Each adverse event must be reported separately. Any medication, whether cardiovascular or not, associated with the treatment of an adverse event must be reported.

Subject deaths are also required to be reported. Refer to Section 12.6. Subject Death for Subject Death collection and reporting requirements.

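### The 4- and 8-week safety and tolerability proportions count study retention, so a subject whose elevated night pacing is stopped for symptoms or safety but who stays in follow-up scores as a success

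*SAP*

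**What the plan says.** The 4-week hypothesis in SAP 7.9.1 is that four weeks of elevated night pacing is safe and tolerable. The scoring rule is: "A variable active4wk will be set to equal 1 for subjects who remain in the study up until the 4 week visit", and 0 otherwise. The 8-week analysis follows the same pattern, "using a variable active8wk to indicate whether a subject remains in the study up until the 8 week visit". Protocol 14.1.1 also words both endpoints as remaining in the study without exiting for symptoms, NT-proBNP, LVEF or troponin.

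The SAP's conservative rule begins "In order to provide the most conservative estimate of the safety and tolerability, any study exit prior to the 4 week visit" and goes on to treat every such exit as a symptom or safety failure. The optional follow-up has the same scope: "sensitivity analysis may be performed, exploring various assumptions regarding ambiguous study exits".

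The protocol handles stopping of pacing in several places:

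- Section 10.15 lists as a reason for exit: "Subject has intolerable symptoms that cannot be alleviated by reprogramming". Section 12.1 likewise asks for related adverse events "for any subject that exits the study because of intolerable symptoms".
- Section 10.19 says of subjects with intolerable symptoms, "whose symptoms cannot be reconciled by reprogramming may have the elevated night pacing programmed OFF", and does not mention exit. Table 9 says pacing will be programmed off if NT-proBNP or troponin worsens, again without mentioning exit.
- Section 10.11 covers an ON subject whose pacing the investigator stops because of abnormal week-4 NT-proBNP, troponin or LVEF: "The subject should continue to be followed through the 12 week visit".
- Section 10.15.4 prefers that randomised subjects be kept in the study.

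**The concern.** Stopping the therapy and leaving the study are separate events in this protocol, but the endpoint sees only the second. A subject who could not safely continue pacing and who stays for follow-up is counted with those who tolerated it. Good retention, which the protocol rightly encourages, then makes the therapy look better tolerated.

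The endpoint carries some weight although it is ancillary. SAP section 6 bases the sample of 30 on the width of its confidence interval and says it will help decide whether to proceed with the therapy.

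**Working it through.** **Step 1: how each route scores.**

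| Event | Where | Outcome in the study | Score |
|---|---|---|---|
| Intolerable symptoms before week 4, subject exits | Protocol 10.15, 12.1 | Exit | active4wk = 0 |
| Same symptoms, pacing switched off, subject stays | Protocol 10.19 (exit not mentioned) | Retained | active4wk = 1 |
| ON subject stopped for abnormal week-4 values | Protocol 10.11 | Followed to week 12 | active8wk = 1 |

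The third row is explicit. The first two are one clinical event with two possible scores, depending on how the site handles it. A biomarker or LVEF stop before week 4 is unlikely: Table 4 schedules no blood draw or echo between baseline and the 4 week visit, so only an unscheduled test could prompt one.

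A subject stopped before week 4 and retained would score 1 on active4wk. The 8-week set then leaves out anyone who withdrew from treatment in the first four weeks, so this subject is a failure in neither proportion. That exclusion is not itself a fault, because Protocol section 14 frames the 8-week question as conditional on the first four weeks having been safe and tolerable.

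**Step 2: the plan's own confidence level.** The SAP states a one-sided 95% lower bound and codes an exact binomial interval with ALPHA=0.1. That gives two-sided 90% limits, so the lower limit has one-sided error 0.1/2 = 0.05. The code agrees with the text.

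**Step 3: size.** The lower bound for x successes in n is the 0.05 quantile of Beta(x, n − x + 1). For x = n it reduces to 0.05^(1/n): 0.05^(1/30) = 0.905 and 0.05^(1/20) = 0.861. As a check, at the bound 0.7614 for 27/30 the probability of 27 or more successes is 0.05.

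Inputs: n = 30 from SAP section 6. An ON arm of 20 is an assumption: 30 × 2/3 under the 2:1 allocation if all 30 are randomised. The number k of subjects stopped but retained is also assumed, since the documents give no rate. With no exits:

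| Setting | k | SAP rule (lower bound) | Stops counted as failures (lower bound) |
|---|---|---|---|
| 8 weeks, ON, n = 20 | 1 | 20/20 = 100% (86.1%) | 19/20 = 95% (78.4%) |
| 8 weeks, ON, n = 20 | 2 | 20/20 = 100% (86.1%) | 18/20 = 90% (71.7%) |
| 4 weeks, n = 30 | 1 | 30/30 = 100% (90.5%) | 29/30 = 96.7% (85.1%) |
| 4 weeks, n = 30 | 3 | 30/30 = 100% (90.5%) | 27/30 = 90.0% (76.1%) |

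The SAP figure does not move with k.

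**Step 4: direction.** With e unrelated exits and k retained stops, the SAP reports (n − e)/n, while the proportion free of a symptom or safety failure is (n − k)/n. The difference is (k − e)/n. For n = 30, e = 2, k = 3 the SAP gives 28/30 = 93.3% against 27/30 = 90.0%, so it is too high. For e = 3, k = 1 it gives 27/30 = 90.0% against 29/30 = 96.7%, so it is too low. Against a count of all exits plus stops, (n − e − k)/n, the SAP figure is always higher by k/n.

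**The case against.** The strongest reply is that the code does what the endpoint says. Protocol and SAP both define it by exit, so there is no derivation error. That is correct, and the gap lies in both documents. It does not make a retention count a measure of whether pacing was safe and tolerable, which is the stated hypothesis.

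The 4-week route is also open to challenge. Section 10.15 states that subjects with unrelieved intolerable symptoms will be exited, whereas section 10.19 describes a device action; both could apply to the same subject. The retention preference in 10.15.4 covers only randomised subjects. This stands, and it is why the 4-week point is no more than an ambiguity.

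Other outputs would show some of these events: adverse event summaries, the CONSORT diagram, crossover records and direct tests of NT-proBNP, troponin and LVEF. They are useful, but they do not change the proportion or its bound.

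Three stronger readings are tempting and are not supported:

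- A reader might infer that the plan by rule counts intolerance before week 4 as success. No passage directs that such subjects be retained.
- A reader might infer that the proportion is inflated overall. Unrelated exits also count as failures, so the net error can go either way.
- A reader might infer that 10.11 and 10.19 contradict each other on abnormal week-4 results. Withdrawal from the study and discontinuing pacing with continued follow-up are alternative discretionary paths.

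**Conclusion.** The point holds for the definition; no stated number is wrong. Both variables measure retention and cannot register a symptom or safety stop in a subject who stays. At week 8 this follows directly from Protocol 10.11. At week 4 it depends on how sites read 10.15 and 12.1 against 10.19 and Table 9. The claim to be the most conservative estimate is true for the handling of exits only, and fails as a general description once one retained stop occurs.

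With no exits, each retained stop is worth 1/20 = 5 points in an assumed ON arm of 20, or 1/30 = 3.3 points at 4 weeks with n = 30. How many there would be is unknown. Severity is minor to moderate: the endpoint is ancillary, unpowered and without a threshold, but it is meant to inform whether the therapy proceeds.

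**What to change.** 1. Set active4wk to 0 for study exit or for elevated night pacing programmed OFF for symptoms or safety before the 4 week visit. Do not count automatic shut-off at the replacement indicator (Protocol 8.4) or reprogramming by clinicians unaware of the study (Table 9).
2. For active8wk, keep every subject of the planned 8-week set in the arm denominators. Score 0 for study exit or for pacing stopped for symptoms or safety after the 4 week visit, including stops under Protocol 10.11, and show those stops as a separate count. State that a stop can be observed only in ON, so the ON–OFF contrast of this proportion is descriptive. Removing the stopped subjects instead would take higher-risk subjects out of ON after randomisation.
3. Report plain study retention by arm alongside, as the like-for-like comparison.
4. Limit the conservative wording to the handling of exits.
5. Record the departure from Protocol 14.1.1 in SAP 7.10.

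The sponsor should also reconcile Protocol 10.15 with 10.19 and Table 9 on whether such subjects exit. This review takes no position on which is right.

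The cost is a revised derivation and one pacing-status flag beside the milestone flags planned in SAP 7.1.3. The reported proportion may be less favourable. The reason for each stop must be classified from crossover, interrogation, adverse event and exit records. The case report forms are under separate cover, so a reason field cannot be confirmed; if there is none, it must be added or the reason obtained by query.
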